## 13.7.3 Analysis Plans for Exploratory Objectives

PD-L1, CD4, and CD8 expression levels in tumor will be correlated with clinical outcomes using logistic and Cox regression methods. Changes over time in microRNA, signature protein expression, immune markers, inflammatory markers, and other markers (e.g. ESR, CRP, vWF, Ferritin, CTLA-4, CD28) will be analyzed with paired t-tests. For BAL samples in the subset of patients with pneunonitis, cytokine, chemokine, and other levels will be described using descriptive statistics and graphs.

A univariate analysis using logistic regression and odds ratio will be utilized to assess for an association between clinical characteristics of those developing grade 2-5 pneumonitis and those who did not. A univariate analysis using logistic regression and odds ratio will be utilized to assess for an association between radiation treatment parameters and pneumonitis.Similar logistic and Cox regression models will be used to correlate other correlative endpoints mentioned above and below with various clinical outcomes.

#### 13.7.3.1 Whole exome sequencing

The whole exome sequencing data will be first examined for quality control by using the software FastQC (Babraham Bioinformatics, Cambridge, UK). Then all qualified sequence reads will be aligned to the human genome (hg19) using BWA MEM aligner. The PCR duplicates will be marked by PICARD MarkDuplicates. The tool PICARD CollectAlignmentSummaryMetrics and CollectHsMetrics will be adopted to assess the coverage across target regions. Analysis-ready BAM files will be generated after base quality recalibration by GATK BaseRecalibrator and PrintReads. Then we will perform variant call on each individual using GATK HaplotypeCaller in GVCF mode. The joint genotyping will be analyzed across all the individuals using GATK GenotypeGVCFs, followed by variant quality recalibration by GATK VariantRecalibrator and ApplyRecalibration on SNPs and INDELs, respectively. Finally, ANNOVAR will be used to annotate variants including refGene, 1000 genome allele frequency, and dbNSFP.

## 13.7.3.2 RNA-seq

The RNA sequencing data will be mapped to the human genome (UCSC hg19) by the software STAR RNA-seq aligner, following the quality control by the software FastQC. The bamutils will assess the reads distribution across the whole genome. Then those uniquely mapped sequencing reads will be summarized as gene expression levels by assigned to hg19 refGene genes using featureCounts. Genes with low read count per million (CPM), e.g. CPM < 0.5 in more than 2/3 of the samples, will be defined as low/non-expressed genes and removed for further analysis. TMM (trimmed mean of M values) method will be used to normalize gene expression data. The software edgeR will be used for differential expression analysis to compare pre-post treatment samples. Differentially expressed genes (DEGs) will be selected by a specific cutoff of false discovery rate (FDR), e.g. FDR < 5%, which will be computed based on multiple test correction of p-values using the Benjamini-Hochberg procedure.

## 13.7.3.3 Proteomics

Similar to RNA-seq analysis, we will compare the gene expression difference at protein level between pre-post treatment samples.

## 13.7.3.4 Lipidomics

Treatment outcome will be initially accessed by multivariate (principle component analyses) statistics using MetaboAnalyst 3.0. The performance of the identified metabolites in discriminating treatment outcome will also be evaluated by constructing receiver operating characteristic curves (ROCs) on the dataset, and estimating the area under the curve (AUC).

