## 9.3.2 Lipidomic Profiling

The Metabolite Profiling Facility at Bindley Bioscience Center (Purdue University) will apply a recently developed mass spectrometry approach for accelerated biomarker discovery named multiple reaction monitoring (MRM)-profiling, which is based on the direct injection (no chromatographic separation) of

diluted lipid and metabolite extracts. By this method, molecules are first detected for each experimental group base on chemical functional groups. In a second step, individual samples are screened for all the molecules detected using a scan mode (MRM) that is very fast and sensitive, resulting in few minutes (15min) of data acquisition for each sample. Statistical analysis will be used to isolate a panel of molecules related to patient response to the treatment. Additional experiments may be necessary to confirm the molecular structure of the informative molecules. Researchers expect that the analysis of these two relevant samples sets by MRM-profiling will be a valuable proof-of-concept for this method as a biomarker-enrichment approach to be added to clinical trials for identifying cohorts of patients who have best changes of benefiting from specific therapies, supporting medical decisions and improving therapeutic success.

MRM-profiling is a two-step strategy for small molecule biomarker identification developed from [name] and [name] (35) (**Figure 1**).

**Figure 1.** MRM-profiling a 2-Step Method. In the first step (discovery) only one representative sample of each experimental group, such as a pooled sample, is interrogated. In the second screening step of MRM-profiling, the entire sample set is interrogated but only for ion pairs (MRMs) detected in the discovery step. MRM measurements are extremely fast and their profiles are used for statistical differentiation of the sample types. In other words, the samples are individually interrogated only for the ion pairs that the representative samples have shown to be characteristic of each class.

Treatment outcome will be initially accessed by multivariate (principle component analyses) statistics using MetaboAnalyst 3.0. The performance of the identified metabolites in discriminating treatment outcome will also be evaluated by constructing receiver operating characteristic curves (ROCs) on the dataset, and estimating the area under the curve (AUC).

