## 13.3 Sample Size and Accrual

This is a non-comparative two-arm trial with each arm being analyzed separately. For Arm 1, when the sample size is 51, a non-parametric test (single-group and based on a non-parametric estimate of the cumulative hazard function) with a one-sided 0.10 significance level will have 80% power to detect an 18 month PFS rate of 44% relative to a historical control rate of 30% (similar to the PACIFIC trial) assuming an accrual period of approximately 24 months and maximum follow-up of 48 months (i.e. would allow for up to 24 months of follow-up after accrual ends). For Arm 2, when the sample size is 48, a non-parametric test (as above) with a one-sided 0.10 significance level will have 80% power to detect an 18 month PFS of 59% relative to a historical control rate of 44% (similar to the PACIFIC trial in the checkpoint inhibitor arm and a 15% increase in absolute magnitude) assuming an accrual period of approximately 24 months. To account for non-evaluable subjects (5%), 54 subjects will be enrolled in Arm 1 and 51 subjects in Arm 2.

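### The lipidomic AUC is estimated on the same subjects used to choose the metabolites, with no resampling stated, so it is biased upward by an amount the documents do not fix

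*Combined protocol and SAP*

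**What the plan says.** Section 9.3.2 (Lipidomic Profiling) describes a two-step assay. In discovery, "only one representative sample of each experimental group, such as a pooled sample, is interrogated". In screening, "the entire sample set is interrogated but only for ion pairs (MRMs) detected in the discovery step". On the aim of the analysis it says: "Statistical analysis will be used to isolate a panel of molecules related to patient response to the treatment". The outcome is therefore used in choosing the panel.

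Section 13.7.3.4 (Lipidomics) gives the statistics, in wording that also appears in 9.3.2. The first step is unsupervised: "Treatment outcome will be initially accessed by multivariate (principle component analyses) statistics using MetaboAnalyst 3.0". Next, "The performance of the identified metabolites in discriminating treatment outcome will also be evaluated", and the method is that this performance is "evaluated by constructing receiver operating characteristic curves (ROCs) on the dataset, and estimating the area under the curve (AUC").

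Neither section states a training and test split, cross-validation, optimism correction, permutation test or independent cohort. Neither gives the number of candidate ion pairs, the panel size, the rule for selecting or combining metabolites, the definition of treatment outcome, or whether the arms are pooled. By contrast, Sections 13.7.3.2 (RNA-seq) and 13.7.3.5 (Methylome) name a false discovery rate cutoff.

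**The concern.** If metabolites are kept because they separate responders from non-responders in a set of patients, their AUC in those same patients includes the luck that got them selected. Any fitted combination adds further optimism. With about 50 patients per arm and possibly many candidates, the inflation can be large.

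The work is exploratory, but Section 9.3.2 gives it an ambitious purpose: a proof of concept for enriching trials with patients likely to benefit and for supporting medical decisions. A reader shown an AUC of 0.8 would take it as promising. Without a corrected estimate or a null reference, that reader cannot tell how much of it comes from selection.

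**Working it through.** The plan gives no AUC, panel size or power for lipidomics, so there is no figure of its own to reproduce. The check asks what the planned calculation returns when no metabolite carries any information.

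**Inputs from the documents**
- Patients: Section 13.3 states that "54 subjects will be enrolled in Arm 1 and 51 subjects in Arm 2". These agree with its 5% allowance: 51/0.95 = 53.7, rounded up to 54, and 48/0.95 = 50.5, rounded up to 51. The total is 105.
- Outcome split: not defined for lipidomics. As stand-ins, the target 18-month PFS rates in 13.3 were used: 44% in Arm 1 and 59% in Arm 2. Pooled: (54 × 0.44 + 51 × 0.59)/105 = 53.85/105 = 0.51.

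**Assumptions not in the documents**
- 20 to 500 candidates, either independent or correlated 0.6 in blocks of 10.
- A panel of the top 1, 3, 5 or 10 by distance of the AUC from 0.5.
- Score by signed sum or linear discriminant.
- Standard normal noise unrelated to outcome; 150 replicates per setting.

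**Hand check for one metabolite.** For one noise marker the AUC has mean 0.5 and standard deviation √[(n₁+n₂+1)/(12·n₁·n₂)]. In Arm 2, 0.59 × 51 ≈ 30, so n₁ = 30 and n₂ = 21, and the standard deviation is √[52/(12 × 630)] = 0.083. The median of the largest |Z| among 100 independent candidates solves (2Φ(z) − 1)¹⁰⁰ = 0.5, so z = 2.70. The best apparent AUC is then about 0.5 + 2.70 × 0.083 = 0.72. The simulation gave 0.72 for this setting.

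**Mean apparent AUC under pure noise (true value 0.50)**

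| Setting | Best single | Panel of 3 | Panel of 5 | Panel of 10 |
|---|---|---|---|---|
| One arm (n = 51 or 54), 20–500 candidates | 0.66–0.76 | 0.68–0.87 | 0.69–0.92 | 0.68–0.97 |
| One arm, 100–200 candidates only | 0.71–0.74 | 0.76–0.84 | 0.78–0.89 | 0.80–0.95 |
| Both arms pooled (n = 105), 20–500 candidates | 0.61–0.68 | 0.63–0.77 | 0.63–0.82 | 0.63–0.89 |

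In the 20–500 rows, low ends are 20 correlated candidates and high ends are 500 independent ones.

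**Same noise, selection repeated inside five-fold cross-validation** (signed-sum score, 100 replicates per setting): means of 0.47 to 0.53 in every setting run, that is, about 0.50.

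**Second simulation.** With 45% responders, a top-5 signed-sum panel and 50, 100 and 500 candidates, the mean apparent AUC was 0.83, 0.86 and 0.91 at n = 51, and 0.74, 0.76 and 0.82 at n = 105. Nested five-fold cross-validation gave 0.50 to 0.51.

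**The laboratory discovery step.** None of the simulations above includes it. In a further check, an outcome-based prefilter applied to all subjects before cross-validation raised the nested noise AUC to as much as 0.65. Nesting only the later statistics is therefore not enough if the discovery pools are formed by outcome.

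**The case against.** Several points on the other side are sound.

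- *Principal components analysis does not use the outcome.* True, and 13.7.3.4 names no classifier or selection rule. But that step is only the initial one. The AUC applies to metabolites already identified, and 9.3.2 says the panel is isolated for its relation to response.
- *The two-step assay separates discovery from testing.* It separates laboratory steps, not patients. The pooled samples are not said to come from other subjects, and the whole sample set is then screened.
- *Computing the AUC on the dataset does not rule out internal resampling.* This stands. The accurate statement is that no resampling is stated, not that the plan excludes it.
- *ROC curves might be drawn for individual metabolites only.* Possible, and the inflation is then smaller: 0.61 to 0.76 in the table.
- *Cross-validation cannot reach the pooled discovery step.* This stands, and the fix has to deal with it.
- *The work is exploratory.* This also stands. No primary or secondary analysis (13.7.1, 13.7.2) and no stopping rule (13.8) uses this AUC.

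A reader might infer two stronger things. One is that noise would show an AUC of about 0.75 to 0.9 whatever the details. The documents do not support this, because the range belongs to small panels from 100 to 200 candidates in one arm, and every one of those inputs is assumed. The other is that the planned AUC could never distinguish a real panel from noise. That goes too far: a value well above a permutation reference would still be evidence. The gap is that no such reference is stated.

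**Conclusion.** The point holds as a flaw in the stated method, with a conditional size. Following the text as written gives a resubstitution AUC that is biased upward. Every mean apparent AUC in the noise simulations was above 0.5, so the direction does not depend on the assumed inputs.

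The amount does. It runs from an apparent 0.61 (single metabolite, arms pooled, few correlated candidates) to 0.97 (ten metabolites, one arm, 500 independent candidates). These figures rest on assumed candidate counts, panel sizes, scoring rules and correlation, and on PFS rates used as a stand-in for an undefined outcome. The consequence is confined to the interpretation of one exploratory analysis. It is still worth correcting, because the better method is known and cheap.

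**What to change.** In both 9.3.2 and 13.7.3.4, replace the AUC sentence with text to this effect:

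> Discrimination will be estimated by repeated cross-validation (or bootstrap optimism correction), with all outcome-based metabolite selection and model fitting repeated inside every resample. The AUC will be reported with a confidence interval and a permutation reference distribution. The apparent AUC will be shown only beside it. The result is hypothesis-generating.

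Add a sentence on discovery: pools will be formed without reference to outcome, or the subjects contributing to them will be excluded from the AUC evaluation.

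Before any outcome-linked analysis, also state the outcome, the selection rule, the panel size and whether arms are pooled. Without these, neither the apparent nor the corrected AUC can be reproduced.

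The cost is a little more analysis and a lower reported AUC. Excluding pooled subjects, if that route is taken, also reduces the evaluation sample. No new subjects, visits or samples are needed, and the primary and secondary analyses are unchanged. The opening of Section 13 allows analysis changes without a protocol amendment unless they alter a significant feature, provided they are documented in the final report.

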## 13.7.3.5 Methylome

All methylation sequencing reads will be mapped to the human genome hg19 by using bowtie2. We then use a software package, bismark, to achieve the methylation information for all sites of CpG, CHG, and CHH, respectively. In this study, we may focus on only CpG methylation. Differentially methylated regions (DMRs) between groups of samples will be determined for false discovery rate (FDR) < 0.05 using methylKit package in R. Identified DMRs will be associated with genes based on their locations.

## 13.7.3.6 Data integration

Based on above individual analysis, we will integrate following sets of genes: (G1) genes with mutations, (G2) DEGs at mRNA level, (G3) DEGs at protein level, and (G4) genes with DMRs. Our aims are (1) to understand how mutations influence on the gene expression at mRNA level and protein level, respectively; (2) to uncover the correlation between mRNA and protein expression; (3) to study the association between mutation and DNA methylation; (4) to find the gene network involved in the mutation and epigenetic regulation.

## 13.7.3.7 Effect of the addition of ipilimumab to consolidation therapy plus nivolumab on PFS.

For exploratory purposes only, we will compare the two treatment arms via a stratified log-rank test to explore the potential effects of the addition of ipilimumab to consolidation therapy plus nivolumab on PFS. The study is not powered to test this exploratory hypothesis; however, as an illustration, a sample size of 51 per group would have 81% power to detect a difference in 18 month survival of .44 in one arm vs .70 in the other arm (hazard ratio of 2.3) using a one-sided log-rank test and alpha level of 0.10.

## 13.7.4 Subgroup Analyses

No subgroup analyses are planned.

## **13.7.5** Other Planned Analyses

We will generate descriptive statistics for demographic and clinical characteristics in the Enrolled Population.

## 13.8 Interim Analysis/Criteria for Stopping Study

After the 10th subject in each arm is treated with at least one dose of study drug and observed for a minimum of 3 months after first dose of study therapy, "unacceptable toxicities warranting early closure of the trial" will be evaluated, defined as a) any definitely related immunotherapy death; or b) any unexpected and previously unreported grade 4 toxicities definitely related to immunotherapy. If such events are observed in one subject, the DSMB will discuss and provide recommendations to the sponsor-investigator whether to terminate the appropriate arm. If such events are observed in two or more of the first 10 subjects, the arm will be terminated. Each arm will be analyzed separately and may result in different actions per arm.

After the 25th subject in each arm is treated with at least one dose of study drug and observed for a minimum of 3 months after first dose of study therapy, "unacceptable toxicities warranting early closure of the trial" will again be evaluated and defined as a) any definitely related immunotherapy death ; or b) any unexpected and previously unreported grade 4 toxicities definitely related to immunotherapy. If such events are observed in two subjects, the DSMB will discuss and provide recommendations to the sponsor-investigator whether to terminate the arm. If such events are observed in three or more of the first 25 subjects, the arm will be terminated. Each arm will be analyzed separately and may result in different actions per arm.

Pneumonitis of grade 3 and 4 will be continuously monitored. An overall rate of 20% or above would be considered unacceptable. If the probability of the grade 3/4 pneumonitis rate being less than 20% drops below 0.1, the arm will be terminated. A priori, the rate is assumed to follow  $\theta \sim beta(1,1)$ . Conditional on observing *y* events out of *n* subjects, the rate follows  $\theta|y,n\sim beta(1+y,1+n-y)$ . The probability of  $\theta < 20\%$  is  $\int_0^{0.2} f(\theta|n, y)d\theta$ . The threshold (k) is defined as the smallest *y* corresponding to the integral being smaller than 0.1, which will lead to termination of the arm.

Ν	10	11	12	13	14	15	16	17	18	19	20	21	22	23	24
k	4	4	4	5	5	5	6	6	6	6	7	7	7	7	8
Ν	25	26	27	28	29	30	31	32	33	34	35	36	37	38	39
k	8	8	8	9	9	9	9	10	10	10	10	11	11	11	11
Ν	40	41	42	43	44	45	46	47	48	49	50	51	52	53	54
k	12	12	12	12	12	13	13	13	13	14	14	14	14	15	15

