## 14.2 Data Safety Monitoring Board

This study will have a Data and Safety Monitoring Board (DSMB). The DSMB is chaired by an independent medical oncologist external to this trial. The DSMB will provide a recommendation to the sponsor-investigator after all information is reviewed. This information will also be provided to BTCRC AHQ who will distribute to the site investigator/participating sites for submission to their respective IRB according to the local IRB's policies and procedures.

The DSMB will meet after the first 10 subjects are treated with at least one dose of study drug and observed for a minimum of 3 months after first dose of study therapy, in each arm respectively. Accrual will not be held while the DSMB review is pending. Each arm will be scrutinized separately and may result in different actions per arm.

The DSMB will also meet after the first 25 subjects are treated with at least one dose of study drug and observed for a minimum of 3 months after first dose of study therapy, in each arm respectively. Accrual will not be held while the DSMB review is pending. Each arm will be scrutinized separately and may result in different actions per arm.

From the time of first subject enrollment until the last subect completes study drug administration, the DSMB will conduct reviews at least twice a year.

The DSMB review will include but is not limited to:

- Study accrual patterns
- Treatment regimen information
- Adverse event summary report
- Summary of any deaths on study including cause of death
- Audit and/or monitoring results, if applicable
- Protocol deviations

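### The 2-of-10 and 3-of-25 termination counts are read only at two scheduled looks with accrual open, so nothing requires randomisation to stop when a count is reached earlier

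*Combined protocol and SAP*

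**What the plan says.** Section 13.8 counts two kinds of event: "any definitely related immunotherapy death" and "any unexpected and previously unreported grade 4 toxicities definitely related to immunotherapy". Each evaluation takes place after the 10th, and again after the 25th, "subject in each arm is treated with at least one dose of study drug and observed for a minimum of 3 months" from first dose.

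Termination is mandatory at a fixed count on each occasion:

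- First look: "If such events are observed in two or more of the first 10 subjects, the arm will be terminated". One event goes to the DSMB for discussion.
- Second look: "If such events are observed in three or more of the first 25 subjects, the arm will be terminated". Two events go to the DSMB for discussion.

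Section 14.2 times the DSMB meetings in the same way and says of both: "Accrual will not be held while the DSMB review is pending". It adds that, until the last subject finishes study drug, "the DSMB will conduct reviews at least twice a year". No count is attached to those reviews.

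A different kind of rule stands beside these in Section 13.8: "Pneumonitis of grade 3 and 4 will be continuously monitored". It has a threshold for every N from 10 to 54.

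**The concern.** The termination rule leaves no discretion at the count. Once a second confirmed event has occurred among the first 10 subjects, waiting for the 10th subject to complete 3 months does not alter the outcome unless an attribution is revised. The waiting period is useful for the one-event and two-event cases, where the DSMB has something to weigh. In an arm that has already reached its count, further subjects can be randomised and dosed although the plan's own criterion for closing the arm is met.

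These are the gravest events that the plan defines. The same section already accepts event-driven closure for grade 3 and 4 pneumonitis. That rule does not fill the gap, because it names only grades 3 and 4 of one toxicity and its table begins at N = 10.

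**Working it through.** **Inputs from the documents.** Enrolment is 54 (Arm 1) and 51 (Arm 2) over about 24 months (Section 13.3). The counts and the 3-month observation are in Section 13.8. Treatment lasts up to 24 weeks (Section 5.1), and adverse events are recorded until 100 days after study drug (Section 12.2.1).

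**Assumptions.** The documents give no rate or timing for these events. I take steady accrual, true event rates of 5% to 20%, and event times uniform over 3 months from enrolment, then over longer windows.

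**The plan's own figures.** 51/0.95 = 53.7, rounded up to 54; 48/0.95 = 50.5, rounded up to 51. Both match. The pneumonitis thresholds, recomputed as the smallest y for which the Beta(1+y, 1+n−y) probability below 0.2 is under 0.1, match all 45 tabulated values. The plan states no operating characteristics for the 2/10 and 3/25 rules, so there is no figure to reproduce there.

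**When the looks fall.** The accrual rate is 54/24 = 2.25 per month in Arm 1 and 51/24 = 2.125 in Arm 2.

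| | Arm 1 | Arm 2 |
|---|---|---|
| First look, month | 10/2.25 + 3 = 7.4 | 10/2.125 + 3 = 7.7 |
| Randomised by then | 10 + 3×2.25 = 16.8 (31% of 54) | 10 + 3×2.125 = 16.4 (32% of 51) |
| Second look, month | 25/2.25 + 3 = 14.1 | 25/2.125 + 3 = 14.8 |
| Randomised by then | 25 + 6.75 = 31.8 (59%) | 25 + 6.375 = 31.4 (62%) |

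DSMB review time comes on top.

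**One worked case.** Suppose that two of the first four subjects in Arm 1 have qualifying events, the fourth subject's being the second to occur. That subject enters at 4/2.25 = 1.8 months, so the event falls between months 1.8 and 4.8. The look is at month 7.4, so the wait is 2.7 to 5.7 months, or 6 to about 13 further subjects.

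**Average lag, by simulation.** Lag is the time of the look minus the time of the deciding event; extra subjects are lag × 2.25. Event rates are 10% to 20%.

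- 10-subject count met: lag about 2.8 to 3.1 months; 2.8×2.25 = 6.3 and 3.1×2.25 = 7.0, so about 6 to 7 subjects. With evenly spaced entry, the mean is 6.2 to 6.9 in Arm 1 and 6.3 to 7.1 in Arm 2.
- 25-subject count met in an arm not stopped at the first look: lag about 3.7 to 4.5 months; 3.7×2.25 = 8.3 and 4.5×2.25 = 10.1, so about 8 to 10 subjects. With evenly spaced entry, the mean is 8.2 to 9.8 and 8.3 to 10.0.

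**Later events.** The recording window is 168 + 100 = 268 days, about 8.8 months. With events uniform over 6 to 8.8 months, the extra subjects fall to about 4 to 5 (10-subject count) and 6 to 9 (25-subject count).

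**How often a count is reached**, if all events fall before the look (binomial):

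| True event rate | P(2 or more of 10) | P(3 or more of 25) |
|---|---|---|
| 2% | 0.016 | 0.013 |
| 5% | 0.086 | 0.127 |
| 10% | 0.264 | 0.463 |
| 20% | 0.624 | 0.902 |

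At 5%, the mean excess when the first count is met is about 5.8 subjects. Averaged over all arms, that is 0.086 × 5.8 = 0.5 subjects.

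**Effect of reading the counts event by event.** With no time limit, a second event among the first 10 that occurs after the first look would close the arm. Under the written rule it would be counted only at the 25-subject look. At a 10% rate, the termination probability would rise from 0.43 to 0.50 with events over 6 months, and from 0.35 to 0.50 over 8.8 months. If only events up to each scheduled look count, the probability is unchanged.

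**The case against.** The strongest reply is that other oversight exists. Sites report SAEs within 1 business day (Section 12.2.2.1), and the sponsor-investigator promptly assesses relatedness and expectedness (12.2.2.3). Investigators review safety continuously (14.1), and the DSMB sees deaths and their causes at least twice a year (14.2). Any of these could close an arm early. If six-monthly reviews acted on the counts, the excess would fall to about 4 to 5 subjects for the first rule and 5 to 6 for the second, on the 3-month event assumption. This stands as a limit on the point: a reader might infer that randomisation is bound to continue, and the documents do not support that. But none of these safeguards carries the counts or an accrual action, so a mandatory rule would depend on discretion.

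A second reply is that a count can fall. Only events judged definite, the top of five relatedness categories (12.1.4), qualify, and grade 4 events must also be unexpected and previously unreported. Attribution may be revised before the look. This also stands, and the fix therefore acts on confirmed events.

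A third is that the events may be rare; Section 11.2.8 describes fatal inflammatory events with ipilimumab as rare. The sizes above apply only when a count is reached.

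A reader might also infer a larger overrun at the second look, 11 to 15 subjects. That figure arises only if arms already terminated at the first look are included, and under the plan those arms never reach the second.

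**Conclusion.** The point holds as a gap in the written rule. Sections 13.8 and 14.2 do not require randomisation to stop when a mandatory termination count is reached before its look. That conclusion rests on the text and not on the simulation.

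The size is conditional: about 6 to 7 subjects after the 10-subject count and 8 to 10 after the 25-subject count, at 10% to 20% event rates with events within 3 months, and fewer if events come later. Faster or slower accrual scales it: 3 months' accrual is 9.0 subjects in Arm 1 if accrual takes 18 months and 4.5 if it takes 36. Nothing here shows that the thresholds 2/10 and 3/25 are wrong. The change is worth making because the events are severe and the cost is small.

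**What to change.** In Sections 13.8 and 14.2, state that up to each scheduled look the existing counts are read as each qualifying event is reported and its attribution confirmed. When a second event among the first 10 treated subjects, or a third among the first 25, is confirmed before that look, the arm's existing termination rule takes effect then instead of waiting for the look.

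Keep the thresholds, the scheduled DSMB meetings and the one-event and two-event discussions unchanged. Limited in this way, the rule stops the same arms as the written rule, only earlier. Sample size and the efficacy analysis are untouched. The cost is a sentence or two in each section, plus event-by-event confirmation of attribution.

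If the sponsor also wants events after the first look to count toward 2 of 10, it should say so and state that this raises the chance of termination, by the amounts shown above.

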## 13.4 Analysis Datasets

Population	Definition
Enrolled	This will comprise all subjects who meet the eligibility criteria and are registered onto the study.
Evaluable	This will comprise all subjects who receive at least one dose of trial drug and either undergo at least one post-baseline assessment or die before any evaluation.
Safety	This will comprise all subjects that take a least one dose of either drug.

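### The pneumonitis stopping rule does not say when a subject enters n; if all treated subjects count, the chance of stopping an arm at a true 20% rate falls from 0.37 to about 0.12–0.34, depending on onset timing

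*Combined protocol and SAP*

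**What the plan says.** Section 13.8 has three safety rules. Two are looks after the 10th and 25th subject in each arm. Both require that the subject has been "observed for a minimum of 3 months after first dose of study therapy", and section 14.2 repeats that condition for the matching DSMB meetings.

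The third rule carries no such condition: "Pneumonitis of grade 3 and 4 will be continuously monitored". The target is explicit: "An overall rate of 20% or above would be considered unacceptable". So is the action: "If the probability of the grade 3/4 pneumonitis rate being less than 20% drops below 0.1, the arm will be terminated". The prior is beta(1,1), the posterior after y events in n subjects is beta(1+y, 1+n−y), and a table gives the threshold k for N = 10 to 54.

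Nothing in 13.8 or elsewhere says whether a subject joins n at first dose, after some minimum observation, or at the end of a risk window. The nearest population is Safety in section 13.4: "This will comprise all subjects that take a least one dose of either drug". The plan does not name it as the denominator of this rule, and it reports no stopping probabilities for the rule.

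**The concern.** A beta-binomial posterior takes every one of the n − y subjects as an observed non-event. Under continuous monitoring during accrual, many have only just started. Section 13.3 implies 54/24 = 2.25 subjects per month in Arm 1. Section 5.1 allows 24 weeks (5.5 months) of treatment, so about 2.25 × 5.5 ≈ 12 subjects per arm could be on treatment at once. If each enters n at first dose, the observed rate is diluted and the boundary is crossed later or not at all.

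The ambiguity can decide a case. Suppose 24 subjects are treated with 7 events, and of the 17 event-free subjects 7 have completed the risk window and 10 are on average halfway. With n = 24 the table gives k = 8, P(θ<0.20) = 0.109, and the arm continues. Counting follow-up completed, n = 7 + 7 + 5 = 19, k = 6, P = 0.032, and the arm closes. Two analysts with the same data could reach opposite decisions on the plan's only numerical boundary for pneumonitis.

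**Working it through.** **Inputs.** Rule, prior and k table: 13.8. Arm sizes: "54 subjects will be enrolled in Arm 1 and 51 subjects in Arm 2" (13.3). Accrual 24 months (13.3). Treatment up to 24 weeks (5.1). Adverse events recorded to 100 days after stopping drug, or to new anti-cancer treatment if earlier (12.2.1). Onset timing of pneumonitis is not in the documents and was varied as an assumption. Entry and first dose were taken as simultaneous.

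**Step 1: the plan's own figure.** k(n) is the smallest y for which the Beta(1+y, 1+n−y) distribution function at 0.20 is below 0.10. At n = 10, y = 3 gives 0.161 and y = 4 gives 0.050, so k = 4. At n = 54, y = 14 gives 0.121 and y = 15 gives 0.069, so k = 15. All 45 printed values reproduce.

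**Step 2: the rule with every outcome known.** An exact recursion runs y through n = 1 to 54, adding a Bernoulli(p) outcome at each step and absorbing at y ≥ k(n) from n = 10.

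| True rate | P(stop), N = 54 |
|---|---|
| 10% | 0.033 |
| 15% | 0.143 |
| 20% | 0.369 |
| 25% | 0.650 |
| 30% | 0.862 |

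For N = 51 at 20% it is 0.364.

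**Step 3: all treated subjects in n.** Simulation used uniform entry over 24 months, n = subjects dosed so far, y = events so far, and 6,000 to 8,000 runs per scenario. Results are for N = 54 and a true rate of 20%.

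| Assumed onset | P(stop) |
|---|---|
| Uniform, 0–1 month | 0.34 |
| Uniform, 0–2 months | 0.29 |
| Uniform, 0–3 months | 0.25 |
| Uniform, 24 weeks | 0.19 |
| Uniform, 24 weeks + 100 days | 0.14 |
| All at 6 months | 0.12 |

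A separate simulation of the one-month case gave 0.31. The relative loss runs from 1 − 0.335/0.369 = 9% (one month) through 1 − 0.185/0.369 = 50% (24 weeks) to 1 − 0.124/0.369 = 66% (all at 6 months). For N = 51 with 24-week onset the figure is 0.207, a loss of 43%. The loss has a limit: once all 54 have matured, a single look at k = 15 has P(X ≥ 15 | 54, 0.20) = 0.107.

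**Step 4: a clearly excessive rate.** At a true 30% with 24-week onset, P(stop) falls from 0.86 to 0.75, and stopping before accrual ends falls from 0.80 to 0.66. About 36 subjects are treated on average, against about 28 with the follow-up-weighted n below.

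**Step 5: a weighted denominator.** Let n(t) = y(t) + Σ min(uᵢ/W, 1), summed over event-free subjects, with uᵢ the time since first dose and W the risk window. This was checked with 4,000 runs per scenario, looks from the tenth treated subject, n rounded up and held at 10 or more, and the printed k.

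- With W equal to the true onset window, P(stop) at 20% was 0.33 to 0.35 across four windows from 1 month to 24 weeks + 100 days. Other ways of handling fractional n gave up to 0.39.
- With 24-week onset, false stops relative to counting all treated rise from about 0.5% to 3% at a true 10%, and from about 5% to 13% at 15%.
- With W fixed at 24 weeks but onset within one month, P(stop) was 0.51 at 20% and 0.25 at 15%. With onset spread to 24 weeks + 100 days it was 0.22 at 20%.
- If weighted n may fall below 10, false stops with 24-week onset rise to about 5% at a true 10% and 17% at 15%.

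**The case against.** The plan never says that just-dosed subjects are scored as event-free. A reader might infer that it does, but the text leaves n undefined, and counting all treated subjects is one reading. That stands, and the figures above are conditional on it.

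A reader might also infer that the chance of stopping is simply halved. The documents do not support that as a fact. Half is the result for onset spread over the treatment period; onset within one month costs about a tenth. And 20% is the boundary rate, where even the matured rule stops only 37% of the time. At 30% the overall loss is about 11 points.

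Copying the 3-month condition from the neighbouring rules looks like the obvious repair, but it has its own bias. If events count at once and event-free subjects only after 3 months, early onset inflates the rate: with onset within one month, simulated stopping at a true 20% was 0.53 to 0.58, and at 15% it was 27 to 28%, against 14% with matured outcomes.

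Other oversight exists: DSMB meetings after 10 and 25 subjects per arm, twice-yearly DSMB reviews that include adverse event summaries (14.2), and continuous investigator review (14.1). This softens the consequence. It does not define n or supply another pneumonitis boundary, and enrolment continues while the DSMB's 10- and 25-subject reviews are pending.

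**Conclusion.** The point holds as a gap in the rule's definition. Section 13.8 applies a posterior that needs known outcomes, under continuous monitoring, without saying when a subject's outcome counts as known; the adjacent rules do say. If all treated subjects count, the chance of stopping was lower than with matured outcomes in every onset scenario tried. At a true 20% it falls from 0.37 to about 0.12–0.34, with 0.19 for onset uniform over 24 weeks and 0.31–0.34 for onset within one month. At a true 30% with 24-week onset it falls from 0.86 to 0.75. These sizes rest on the assumed onset windows, uniform accrual over 24 months and 54 subjects in the arm. The k table is correct and is not in question.

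**What to change.** In 13.8, define n. Each subject with a grade 3 or 4 event counts as one. Each event-free subject counts by the fraction completed of a risk window stated in advance, for example the 24-week treatment period. Apply the same criterion, P(θ<20%) < 0.1, from the tenth treated subject, and say how fractional n is handled, including that n is taken as no less than 10, where the table begins. State that four events before the tenth subject meet the boundary at once, since k = 4 at N = 10 makes crossing certain. Keep the plan's grade 3 and 4 event definition. Report stopping probabilities over a range of true rates and onset assumptions.

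The cost is a paragraph of SAP text and a small simulation. False stops rise relative to counting all treated, but only to about the matured table's own 3.3% at a true 10% and 14.3% at 15%. The weighting depends on the window: a 24-week window over-stops if onset is much earlier and under-stops if much later, so the choice should be justified and its sensitivity shown.
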